6.3.2 Blinding and Code-breaking Procedures

The study will be performed in a modified double-blind fashion:

- Participant, Investigators/sub-investigator/staff involved in the sampling, the immunogenicity assays and safety assessment will not know which vaccine is administered.
- Only the study site staff who prepare and administer the vaccine and are not involved with the safety evaluation will know which vaccine is administered

The code may be broken in the event of an AE only when the identification of the vaccine received could influence the treatment of the participant. Code-breaking should be limited to the participant(s) experiencing the AE.

The blind can be broken by the Investigator or a delegate through the IRT system, as explained in the code-breaking procedures described in the Operating Guidelines. Once the emergency has been addressed by the site, the Investigator or a delegate must notify the Sanofi Pasteur Responsible Medical Officer if a participant's code was broken. All contact attempts with the Sponsor prior to unblinding are to be documented in the source documents, and the code-breaking CRF is to be completed.

The Independent Ethics Committee (IEC)/Institutional Review Board (IRB) must be notified of the code-breaking, in accordance with local regulations. All documentation pertaining to the event must be retained in the site's study records and in the Sanofi Pasteur files. Any intentional or unintentional code-breaking must be reported, documented, and explained, and the name of the person who requested it must be provided to the Sponsor.

A request for the code to be broken may also be made by the Global Pharmacovigilance (GPV) Department through an internal system for reporting to Health Authorities in the case of an unexpected SAE considered causally related, as described in International Council for Harmonization (ICH) E2A^a. In this case, the code will be broken only for the participant(s) in question. The information resulting from code-breaking (ie, the participant's vaccine or group assignment) will not be communicated to either the Investigator or the immediate team working on the study, except for the GPV representative.

The code-breaking procedures are described in the Operating Guidelines.

6.4 Study Intervention Compliance

The following measures will ensure that the study intervention is administered as planned (see Table 6.1) and that any non-compliance is documented so that it can be accounted for in the data analyses:

- All vaccinations will be administered by qualified and trained study personnel.
- The person in charge of study intervention management at the site will maintain accountability records of study intervention delivery to the study site, study intervention inventory at the site, dose(s) given to each participant, and unused or wasted doses.

6.5 Concomitant Therapy

At the time of enrollment, all ongoing medications, and other therapies (eg, blood products) should be recorded in the CRF as well as new medications prescribed for new medical conditions/AEs during study participation.

All medications will be reportable and will be collected in the CRF until last contact date of the participant.

Dosage, administration route and indication will be collected in the e-CRF.

Medications given in response to an AE will be captured in the "Action Taken" section of the AE CRF. Medications will not be coded.

6.5.1 Rescue Medicine

Appropriate medical equipment and emergency medications, including epinephrine (1:1000), must be available on site in the event of an anaphylactic, vasovagal, or other immediate allergic reaction.

6.6 Dose Modification

Not applicable.

6.7 Intervention After the End of the Study

Not applicable.

^a All unexpected and related SAEs submitted to European Union competent authorities must be unblinded.

7 Discontinuation of Study Intervention and Participant Discontinuation/Withdrawal

7.1 Discontinuation of Study Intervention

Not applicable as there is only one vaccination.

7.2 Participant Discontinuation/Withdrawal from the Study

- A participant may withdraw from the study at any time at his/her own request or may be withdrawn at any time at the discretion of the Investigator for safety, behavioral, compliance, or administrative reasons. This is expected to be uncommon.
- The reason for withdrawal should be clearly documented in the source documents and in the CRF: AE, Lost to Follow-up, Protocol Deviation, or Withdrawal by Participant.
- The participant will be permanently discontinued both from the study intervention and from the study at that time.
- If the participant withdraws consent for disclosure of future information, the Sponsor may retain and continue to use any data collected before such a withdrawal of consent.
- If a participant withdraws consent, he/she may request destruction of any samples taken and not tested, and the Investigator must document this in the site study records.
- Withdrawn participants may be replaced.

Follow-up of Discontinuations

For participants who have prematurely terminated the study, the site should attempt to contact them and complete all scheduled safety follow-ups, except if they specified that they do not want to be contacted again and it is documented in the source document.

For participants where the reason for early termination is lost to follow-up, the site will not attempt to obtain further safety information. See Section 7.3 for the definition of "lost to follow-up".

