7.3 Lost to Follow-up

A participant will be considered lost to follow-up if he or she repeatedly fails to return for scheduled visits and is unable to be contacted by the study site.

The following actions must be taken if a participant fails to return to the site for a required study visit or cannot be contacted as planned in the SoA:

• The site must attempt to contact the participant and reschedule the missed visit as soon as possible and counsel the participant on the importance of maintaining the assigned visit

schedule and ascertain whether or not the participant wishes to and/or should continue in the study.

- Before a participant is deemed lost to follow-up, the Investigator or designee must make every effort to regain contact with the participant (where possible, 3 telephone calls and, if necessary, a certified letter to the participant's last known mailing address or local equivalent methods), or at least to determine his/her health status while fully respecting his/her rights. These contact attempts should be documented in the participant's medical record.
- Should the participant continue to be unreachable, he/she will be considered to have withdrawn from the study.

Discontinuation of specific sites or of the study as a whole are handled as part of the Appendix 10.1.

8 Study Assessments and Procedures

- Study procedures and their timing are summarized in the SoA. Protocol waivers or exemptions are not allowed.
- Immediate safety concerns should be discussed with the Sponsor immediately upon occurrence or awareness to determine if the participant should continue or discontinue study intervention.
- Adherence to the study design requirements, including those specified in the SoA, is essential and required for study conduct.
- All screening evaluations must be completed and reviewed to confirm that potential participants meet all eligibility criteria. The Investigator will maintain a screening log to record details of all participants screened and to confirm eligibility or record reasons for screening failure, as applicable.

Blood samples will be collected as described in the SoA table (Section 1.3). At Visit 1 (BL0001) and Visit 2 (BL0002), 10 mL of blood will be collected in tubes provided by or recommended by the Sponsor.

Guidance and information for the sample collection, preparation, storage, and shipment are provided in the Operating Guidelines.

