3.3 Populations for Analysis

The following populations for analysis are defined:

Safety Analysis Set (SafAS)

Safety Analysis Set (SafAS): Participants who have received a dose of the study vaccines. All participants will have their safety analyzed according to the vaccine they actually received. Safety data recorded for a vaccine received out of the protocol design will be excluded from the analysis (and listed separately). SafAS will be used for safety analyses.

Full analysis set (FAS)

Full analysis set (FAS): Subset of randomized participants who received a dose of the study vaccine and had a post-vaccination blood sample. Participants will be analyzed according to the intervention to which they were randomized. The FAS will be used for immunogenicity analysis.

Per-protocol analysis set (PPAS)

Per-protocol analysis set (PPAS): Subset of the FAS. Participants presenting with at least one of the following conditions will be excluded from the PPAS:

- Participant did not meet all protocol-specified inclusion criteria or met at least one of the protocol-specified exclusion criteria
- Participant did not receive vaccine
- Participant received a vaccine other than the one that he/she was randomized to receive
- Preparation and/or administration of vaccine was not done as per-protocol
- Participant did not receive vaccine in the proper time window
- Participant did not provide the post-dose serology sample at Visit 2 in the proper time window, or a post-dose serology sample was not drawn
- Participant received a protocol-prohibited therapy/medication/vaccine

PPAS will be used for immunogenicity analysis.

Participants with data in CRF

Participants with data in CRF: Participants with data in CRF are participants for whom data were recorded at a visit.

Randomized participants

Randomized participants: a randomized participant is a participant for whom a randomized group has been allocated by IRT.

Participants with data in CRF and randomized participants will be used to summarize participants' disposition, demographic and baseline characteristics.

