3.4.2.2 Safety

The following safety data will be summarized using Clopper-Pearson method to estimate the 95% CI by age subgroup, intervention group and pooled age subgroups. The current Medical Dictionary for Regulatory Activities (MedDRA) version will be used for the coding of all AEs/reactions.

Solicited Reactions

Number and percentage of participants with:

- Presence of solicited injection site reactions and solicited systemic reactions occurring up to 7 days after injection
- Each solicited reaction according to time of onset, maximum intensity, and number of days of occurrence and action taken

Unsolicited Events and Reactions

Number and percentage of participants with:

- Any unsolicited immediate systemic event in the 30 minutes after injection according to System Organ Classes (SOC) and Preferred Terms (PT)
- Any unsolicited event and reaction 28 days after injection according to SOC and PT
- Any unsolicited event/reaction according to time of onset, maximum intensity, and duration

SAEs

Number and percentage of participants with:

• Any SAE within 28 days after injection and throughout the entire study according to SOC and PT, seriousness, and outcome

AESIs

Number and percentage of participants with:

• Any AESI within 28 days after injection and throughout the entire study according to SOC and PT, seriousness, and outcome

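### A participant recorded as lost to follow-up before D181 gets no 6-month safety call, yet apparently stays in the whole-study SAE/AESI denominator (minor)

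*Protocol*

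**What the plan says.** **Contact after early termination.** For participants who stop early, Protocol 7.2 says "the site should attempt to contact them and complete all scheduled safety follow-ups", unless they have asked not to be contacted. One group is then taken out of that rule: "For participants where the reason for early termination is lost to follow-up, the site will not attempt to obtain further safety information." The reader is sent to 7.3 for the definition.

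**Definition and search.** Under Protocol 7.3 a participant is lost if he or she "repeatedly fails to return for scheduled visits and is unable to be contacted by the study site". A search comes first: "Before a participant is deemed lost to follow-up, the Investigator or designee must make every effort to regain contact with the participant", which means "where possible, 3 telephone calls and, if necessary, a certified letter", or at least finding out the person's health status, with the attempts documented. If that fails: "Should the participant continue to be unreachable, he/she will be considered to have withdrawn from the study."

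**Schedule.** Table 1.1 of the protocol has two visits (D01, D29) and two calls (D08, D181). SAEs and AESIs are collected to D181, and their presence throughout the trial is one of the safety endpoints under the primary objectives.

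**Analysis.** SAP 3.3 defines the safety analysis set as "Participants who have received a dose of the study vaccines". SAP 3.4.2.2 reports the number and percentage with "Any SAE within 28 days after injection and throughout the entire study according to SOC and PT, seriousness, and outcome", and the same for AESIs, with Clopper-Pearson intervals. Missing safety data are generally not replaced (SAP 3.4.3.1). The rule that removes participants without data from a denominator, in SAP 4.2.1.1.3, is written for solicited reactions only.

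**The concern.** The 7.2 exception works as a permanent stop. Someone who could not be reached around D29 may well be reachable at D181, but the site is told not to try. That call is the only planned way of learning about SAEs and AESIs in the last five months or so of follow-up.

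The analysis side does not show the gap next to the result. If membership of the denominator needs only a dose, the lost participant adds one to the denominator and, after the loss, nothing to the numerator. The 6-month percentage is pulled down and its upper confidence limit is a little too low. A reader of the SAE and AESI tables would not see how many of the 150 per vaccine group were actually asked.

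**Working it through.** **1. The plan's own figure.** Protocol 9.2 plans 75 per age-by-vaccine cell and 5% drop-out: 75 × 0.95 = 71.25, so 71 evaluable. This reproduces. So do the four precision figures at n = 71:
- Clopper-Pearson width 24.2%;
- Wilson-score width for a difference 32.0%;
- t-based half-widths 0.154 and 0.216 with SD 0.65.

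None of these is in dispute. The 5% is used below only as a scale for possible loss.

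**2. The text in time order.**
- Visit 1 is the vaccination visit, so Visit 2 (D29) is the only visit to which a participant returns. The repeated-failure wording in 7.3 therefore sets little delay, and no minimum period is given.
- A search made soon after D29 can find events up to that date. It cannot find events in the months that follow.
- Once the label is recorded, 7.2 removes the D181 call. D29 to D181 is 152 of the 180 days of follow-up.

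**3. The denominator.** The safety set has no follow-up condition, missing data are not replaced, and no person-time or completeness rule is written for SAEs or AESIs. The participant therefore stays in the whole-study percentage. This is an inference from those three facts; the SAP does not state it.

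**4. Size of the understatement.** Assumptions: a share d of participants is lost at D29, events up to D29 are captured, and the hazard is constant and the same in lost and followed participants. For small risks, the share of the true 6-month risk captured is

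(1 − d) + d × 28/180 = 1 − d × 152/180.

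- d = 5%: 1 − 0.0422 = 0.958, about 4% relative understatement.
- d = 10%: 1 − 0.0844 = 0.916, about 8%.

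The exponential form gives the same answer for true risks of 1%, 2% and 5%. For a true 2%, the reported figure is 1.92% at 5% loss and 1.83% at 10% loss.

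The diary card is collected at Visit 2, so the last completed scheduled contact could be the D08 call. The missing share is then 173/180, and the understatement is 0.05 × 173/180 = 4.8% or 0.10 × 173/180 = 9.6%. Under these assumptions it cannot exceed d.

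**5. Effect on the interval, per vaccine group of 150.** 5% of 150 is 7.5, taken as 8 lost (142 followed); 10% is 15 lost (135 followed). With zero events the Clopper-Pearson upper limit is 1 − 0.025^(1/n).

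| Denominator | 0 events, upper limit | 3 events, % (95% CI) |
|---|---|---|
| 150 (safety set) | 2.43% | 2.00 (0.41–5.73) |
| 142 (5% lost) | 2.56% | 2.11 (0.44–6.05) |
| 135 (10% lost) | 2.70% | 2.22 (0.46–6.36) |

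The smaller denominators treat the lost participants as giving no information at all, although they do give some up to the loss. The first row and the row for the assumed loss therefore bracket the answer.

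**The case against.** **The search in 7.3.** A reader might infer from the 7.2 sentence alone that sites need not look for someone who merely misses Visit 2. That is wrong. The label needs failed contact and a documented effort that extends to health status. A participant absent through serious illness is just the person that step is meant to find, and the documents give no support for classing someone as lost after a set few weeks. This answers the concern for the period up to the search, but not for the months after it.

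**A conflict between 7.2 and 7.3.** A reader might also see a contradiction, because 7.3 treats lost participants as withdrawn and 7.2 asks sites to contact early terminators. There is none. Loss to follow-up is one of the listed withdrawal reasons, and the 7.2 sentence is an explicit exception for it.

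**Counted as event-free.** The SAP does not say this. SAEs reported before the loss or found during the search still count. Participants are asked to notify the site of potential SAEs at any time (Protocol 4.1), and related SAEs learned of after discharge must be reported (Protocol 8.3.1). The supported statement is that no event is counted after the loss unless it is spontaneously reported.

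**Completeness is visible elsewhere.** Completion of the 6-month follow-up is defined (Protocol 4.4) and has its own CRF record (Table 1.1), and the SAP plans a disposition and follow-up description. A reader could probably find the count. It is still not placed beside the percentages that depend on it.

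**Small and symmetric.** The study is descriptive, tests nothing, and applies the rule alike in both arms. Even with 0% loss in one arm and 10% in the other at a true 2%, the reported risks would be 2.00% and 1.83%, far inside the interval of 0.41–5.73% for 3/150. This stands, and it sets the severity.

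**Conclusion.** The point holds as a minor one. The protocol bars the only scheduled contact after D29 for participants labelled lost before D181, and nothing in 7.3 delays the label until then. The SAE/AESI denominator that keeps them in is inferred.

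The relative understatement is about 4% if the entire 5% drop-out is loss at D29, and about 8% at 10% loss. The zero-event upper limit per vaccine group moves from 2.43% to 2.56% or 2.70%. The documents do not say how much of the drop-out is loss to follow-up, so these figures show scale only. If serious events are more common among the lost, the understatement is larger, but the documents give no rate from which to size that. No alpha, power or planned precision figure changes.

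**What to change.** **Protocol 7.2.** Replace the lost-to-follow-up sentence with wording such as: *For participants lost to follow-up before D181, the site will still attempt the scheduled D181 phone call to ascertain SAEs and AESIs, unless the participant declined contact.* The search duty in 7.3 stays as it is.

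**SAP 3.4.2.2.** Beside the whole-study SAE and AESI percentages, show by age and vaccine group the number with a completed 6-month contact. Keep the safety set as the main denominator: a completers-only percentage would discard what was learned before loss.

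**Cost.** At 5% drop-out, 5% × 300 = 15, so at most about 15 calls, all already in the schedule, and one added count per table from a CRF record that exists. Some calls will fail, so the gap will shrink and not close.

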7.3 Lost to Follow-up

A participant will be considered lost to follow-up if he or she repeatedly fails to return for scheduled visits and is unable to be contacted by the study site.

The following actions must be taken if a participant fails to return to the site for a required study visit or cannot be contacted as planned in the SoA:

• The site must attempt to contact the participant and reschedule the missed visit as soon as possible and counsel the participant on the importance of maintaining the assigned visit

schedule and ascertain whether or not the participant wishes to and/or should continue in the study.

- Before a participant is deemed lost to follow-up, the Investigator or designee must make every effort to regain contact with the participant (where possible, 3 telephone calls and, if necessary, a certified letter to the participant's last known mailing address or local equivalent methods), or at least to determine his/her health status while fully respecting his/her rights. These contact attempts should be documented in the participant's medical record.
- Should the participant continue to be unreachable, he/she will be considered to have withdrawn from the study.

Discontinuation of specific sites or of the study as a whole are handled as part of the Appendix 10.1.

8 Study Assessments and Procedures

- Study procedures and their timing are summarized in the SoA. Protocol waivers or exemptions are not allowed.
- Immediate safety concerns should be discussed with the Sponsor immediately upon occurrence or awareness to determine if the participant should continue or discontinue study intervention.
- Adherence to the study design requirements, including those specified in the SoA, is essential and required for study conduct.
- All screening evaluations must be completed and reviewed to confirm that potential participants meet all eligibility criteria. The Investigator will maintain a screening log to record details of all participants screened and to confirm eligibility or record reasons for screening failure, as applicable.

Blood samples will be collected as described in the SoA table (Section 1.3). At Visit 1 (BL0001) and Visit 2 (BL0002), 10 mL of blood will be collected in tubes provided by or recommended by the Sponsor.

Guidance and information for the sample collection, preparation, storage, and shipment are provided in the Operating Guidelines.

8.1 Efficacy and Immunogenicity Assessments

8.1.1 Efficacy Assessments

No clinical efficacy data will be obtained in the study.

8.1.2 Immunogenicity Assessments

The HAI assay is the main test that detects Ab directed against the HA antigen and is commonly used to assess the immunogenicity of influenza vaccines. HAI Ab titers to each virus strain represented in the vaccine will be measured in sera obtained at baseline (D01) and 28 days after immunization (D29).

All methods will be performed at a Sanofi Pasteur laboratory or at a qualified contract laboratory under Sanofi Pasteur's responsibility, as described below. Test serum samples and quality control sera (sheep, ferret, and / or human sera) are incubated with Sigma Type III neuraminidase (NA) from *Vibrio cholerae* to eliminate non-specific inhibitors. Adsorption of spontaneous anti-species agglutinins are then performed by incubating the test serum samples and quality control sera with a red blood cell (RBC) suspension. Following this, the mixtures are centrifuged and the supernatants containing the treated sera are collected for testing. Ten 2-fold dilutions (starting at 1:10) of the treated test serum samples and quality control sera are incubated with a previously titrated influenza antigen at a concentration of 4 hemagglutination units (HAU) / 25 μ L. Influenza antigen is not added to the serum control wells containing only serum and RBCs. The mixture is then incubated and a RBC suspension is added. Following incubation, the results are read. The

endpoint of the assay is the highest serum dilution in which complete inhibition of hemagglutination occurred. Each serum sample can either be tested in singleton (ie, one assay run) or in 2 independent assay runs (duplicate) which will include 2 independent samplings of the original serum and 2 independent preparations of influenza virus antigen. The lower limit of quantitation (LLOQ) is set at the lowest dilution used in the assay, 1:10. Titers below this level are reported as < 10 (1/dilution [dil]). If the highest / last serum dilution used in the assay exhibited complete inhibition of hemagglutination, the serum Ab titer is reported as $\ge 10 240$ (1/dil).

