3.6 Data Monitoring Committee (DMC)

Not applicable.

4 Complementary Information on Assessment Methods

Study assessments and procedures are detailed in Section 8 of the protocol. This section focusses on complementary/additional information not detailed in the protocol.

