4.2.3 Immunogenicity

4.2.3.1 Computed Values for Analysis

In order to appropriately manage extreme values (< LLOQ and \geq ULOQ) for analysis purposes, the following computational rule is applied to the values provided in the clinical database for each blood sample (BL) drawn:

- If a value is < LLOQ, then use the computed value LLOQ/2
- If a value is between \geq LLOQ and < ULOQ, then use the value
- If a value is \geq ULOQ, then use the computed value ULOQ

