4.2.3.2 Fold-rise

The derived endpoint fold-rise is driven by both baseline and post-baseline computed values

as described in Section 4.2.3.1 and is computed as follows:

• Calculate the fold-rise of values as the ratio of post-baseline computed value divided by baseline computed value

For HAI assay, if the computed value is \geq 4-fold rise, then the derived \geq 4-fold rise indicator will be "Yes" for that test, otherwise \geq 4-fold rise will be "No".

Note: If baseline or post-baseline is missing, then the fold-rise is missing.

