4.2.3.3 Seroconversion

Seroconversion is defined for HAI assay as either computed titer value < 10 (1/dilution [1/dil]) at D01 and post-injection computed titer value ≥ 40 (1/dil) at D29, or computed titer value ≥ 10 (1/dil) at D01 and a ≥ 4 -fold increase in computed titer value (1/dil) at D29.

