Confidential/Proprietary Information Page 23 of 27 distributions reasonably diffuse (essentially non-informative on the log₁₀ scale). Given a hypothetical observed data with $\delta = 0, \mu = 2.5, \sigma = 0.65$, the prior distribution and marginal posterior distribution of δ is shown in Appendix Figure 1. It is shown that these priors are so vague that the likelihood (the data contribution) has a strong influence on the posterior distribution estimation.

[figure not shown]
Parameter	value
μ_0	2.0
γ_0^2	12
δ_0	- 0.176/2
$ au_0^2$	10 ²

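### Protocol 8.1.2 contradicts itself: ten 2-fold dilutions from 1:10 end at 1:5120, yet complete inhibition at the last one is reported as at least 10 240, which takes eleven

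*Protocol*

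**What the plan says.** Protocol 8.1.2 makes four statements about the HAI assay:

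- The sera are tested at "Ten 2-fold dilutions (starting at 1:10) of the treated test serum samples and quality control sera".
- "The lower limit of quantitation (LLOQ) is set at the lowest dilution used in the assay, 1:10". So 1:10 is itself one of the dilutions tested.
- The titer is the highest dilution that still shows complete inhibition.
- "If the highest / last serum dilution used in the assay exhibited complete inhibition of hemagglutination, the serum Ab titer is reported as" at least 10 240 (1/dil).

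The section also lets each serum be tested once or in two independent runs. It does not say how two runs are combined.

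SAP Section 4 gives no dilution series of its own and defers to the protocol: "Study assessments and procedures are detailed in Section 8 of the protocol". SAP 4.2.3.1 says that "the following computational rule is applied to the values provided in the clinical database for each blood sample (BL) drawn". Under that rule a value at or above the ULOQ is set to the ULOQ, but the SAP gives no number for it. SAP 4.2.3.2 then says "Calculate the fold-rise of values as the ratio of post-baseline computed value divided by baseline computed value", and SAP 4.2.3.3 likewise defines seroconversion from computed values.

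**The concern.** The dilution count and the reporting ceiling cannot both be right. The ceiling matters because 10 240 is the only upper value in either document, so it is the number an analyst will use as ULOQ in SAP 4.2.3.1. From there it enters the GMT, the GMFR, the 4-fold-rise indicator and seroconversion, all of which belong to the primary immunogenicity analysis.

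If the laboratory runs ten dilutions as written, a serum fully inhibited at 1:5120 is known only to have a titer of at least 5120 but is coded as 10 240. Some participants could then be counted as 4-fold responders when the assay has shown only a rise of at least 2-fold.

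**Working it through.** **Inputs.** From Protocol 8.1.2: ten dilutions, 2-fold step, first dilution 1:10, ceiling 10 240. From Protocol 9.2 and SAP 3.2: 71 evaluable per age and vaccine group, SD 0.65, half-widths 0.154 (single mean) and 0.216 (difference). From SAP Appendix 2: mean 2.0 (prior mean) and 2.5 (hypothetical data), both log10. Assumed here: normal log10 titers, and baseline means of 1.5 and 2.0. The documents give no expected baseline mean.

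**1. Trying to reproduce 10 240.** The k-th dilution is 10 × 2^(k−1).

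- Ten dilutions from 1:10: 10, 20, 40, 80, 160, 320, 640, 1280, 2560, 5120. The last is 5120.
- Number needed to reach 10 240: log2(10 240/10) + 1 = 11.
- Ten dilutions ending at 10 240 would start at 10 240/2^9 = 20, against the stated start and LLOQ of 1:10.
- Reporting one step above the last inhibiting dilution gives 2 × 5120 = 10 240, against the section's own definition of the endpoint.
- Ten doublings after 1:10 give 10 × 2^10 = 10 240, but that is eleven dilutions.

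No reading satisfies all four statements.

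**2. Effect on a GMT if ten are run.** Let f be the share of sera capped, f = 1 − Φ((log10 5120 − mean)/0.65), with log10 5120 = 3.709. Coding these sera 10 240 instead of 5120 multiplies the GMT by 2^f.

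| Mean log10 | f | Sera of 71 | 2^f |
|---|---|---|---|
| 2.0 | 0.43% | 0.30 | 1.003 |
| 2.5 | 3.14% | 2.23 | 1.022 |

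For scale, the planned half-width for a single mean is a factor of 10^0.154 = 1.43.

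**3. Effect on the GMT ratio.** The ratio is multiplied by 2^(f1−f2), where f1 and f2 are the capped shares in the two arms. It is unchanged only if they are equal. As an illustration, with the two shares above in opposite arms, 2^(0.0314−0.0043) = 1.019. The planned half-width for a difference is a factor of 10^0.216 = 1.64.

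**4. Effect on seroconversion, single-run readings, D29 capped.**

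| D01 reading | Ratio with 10 240 | Ratio with 5120 | Status changes? |
|---|---|---|---|
| 1280 | 8 | 4 | No |
| 2560 | 4 | 2 | Yes |
| Capped | 1 | 1 | No |

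Below 1280 both ratios exceed 4. The share of sera with a D01 reading of 2560 is Φ((log10 5120 − m)/0.65) − Φ((log10 2560 − m)/0.65). This is 0.13% (0.09 of 71) at m = 1.5 and 1.09% (0.77 of 71) at m = 2.0. For single-run readings these are upper bounds on changed status, because the D29 titer must also be capped.

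**5. Duplicate runs.** Suppose two runs are combined by geometric mean, which is an assumption. D01 readings of 1280 and 2560 give √(1280 × 2560) ≈ 1810. Then 10 240/1810 = 5.7 but 5120/1810 = 2.8, so status changes there too. The restriction to 2560 holds only for single-run readings.

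**6. Threshold endpoints.** Both candidate ceilings lie far above 10 and 40, so those endpoints do not change.

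**The case against.** The strongest reply is that *ten* is loose wording for ten doublings after 1:10. Eleven dilutions are then run, 10 240 is exactly right, and the only defect is one word in an assay description. The documents cannot exclude this, and every numerical consequence above depends on its being false. The text mismatch remains either way.

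A reader might infer that the ULOQ is undefined because the SAP gives no number. The documents do not support that. SAP Section 4 sends the analyst to Protocol Section 8, where 10 240 is the single upper reporting value, and the dilution count enters no SAP formula.

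A reader might also infer that capped sera have been coded a factor of 2 too high and that the primary immunogenicity results are biased. That is not shown either. It needs ten dilutions actually to be run, which only the assay procedure can settle. Even then, the figures compare two capping conventions and do not measure bias against the true GMT, because the true titers of capped sera are unknown.

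It is also fair to say that the inputs are illustrative: 2.0 is the centre of a diffuse prior and 2.5 belongs to a made-up example. They indicate the order of the effect and do not predict it.

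**Conclusion.** The inconsistency is real and lies wholly within Protocol 8.1.2. No other section restates or repairs either figure, and the documents do not show which is wrong. Severity is minor.

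With eleven dilutions the effect is zero. With ten, the choice of ceiling moves a GMT by about 0.3% to 2.2% under the stated normal model, well inside the planned precision. It would alter seroconversion for fewer than one serum in 71, given single-run readings and the assumed baseline means. Duplicate runs could add intermediate baselines to the affected set. The analyses are descriptive and no success threshold is set for the Bayesian probability, so no formal decision turns on the ceiling. The case for correcting it is that it sets the upper end of the primary assay's range.

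**What to change.** Before database lock, check the assay procedure for the number of dilutions incubated. Then do one of two things:

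- correct the count in Protocol 8.1.2 to eleven (1:10 to 1:10 240) and keep the ceiling at 10 240 or more; or
- keep ten dilutions and report the ceiling as 5120 or more.

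Use the same number as the ULOQ when SAP 4.2.3.1 is applied. The cost is one word or one number in the protocol, and no new assays.
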